6.7 Prior and Concomitant Medications

All prescription, nonprescription medications (e.g., over-the-counter [OTC]) drugs and herbal supplements) and non-medical treatments starting from 30 calendar days before Screening until end of the study must be recorded in source documents and the eCRF. For each medication, documentation should list the trade or generic name, the total daily dose including units (or the dose, units, and scheduled and actual frequency of administration if the medication is not taken daily), the route of administration, and the reason for use.

Changes, additions, or discontinuations to medications will be assessed and recorded in the eCRF during each study visit. All as-needed prescriptions should be converted to reflect actual dose taken per day.

Starting on the first day of the screening phase, after written informed consent for the study has been provided, all antipsychotic or other psychotropic medications will be stopped with clinically appropriate titration down as per the Investigator's clinical judgment. Patients will be

Confidential Page 49 of 102

instructed not to take any medication(s) during the conduct of the study unless approved by the Investigator. Any patient unable to be safely discontinued from current antipsychotic therapy or other psychotropic medications will not be eligible for the study. Any treatment other than the study treatment given will be considered a concomitant medication and will be documented in the eCRF. Any patient requiring emergency treatment with prescription or nonprescription medication during the screening phase through the EoS Visit will be approved by the Investigator. If the Investigator determines that the patient requires medication during the study, the Medical Monitor must be contacted within 24 hours.

Psychotropic medications are prohibited except for lorazepam as needed for agitation, restlessness, irritability, or hostility; zolpidem, zaleplon, or eszopiclone for insomnia; diphenhydramine or benztropine for EPS; and propranolol for akathisia.

Within the daily limits shown in 2, lorazepam, benztropine, and propranolol are not allowed on as needed basis; every administration must be considered and approved by the Investigator prior to administration.

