The AE associated with the need for lorazepam, benztropine, or propranolol should be recorded on the Adverse Events in the eCRF. The amount and timing for each lorazepam, benztropine, or propranolol administration should be recorded for each patient.

Table 6.2:	Permitted	concomitant	medications

Medication	Study Period	Dose Permitted	Timing Restriction			
	Screening phase through Day 7	Maximum of 6 mg/day				
	Day 8 though Day 14	Maximum of 4 mg/day	Not within 12 hours prior to PANSS			
Lorazepam	Day 15 through Day 28	Maximum of 2 mg/day On no more than 4 days/Week				
Benztropine	Screening phase Through Day 28	Maximum 4 mg/day	Not within 12 hours prior to SAS, BARS, or AIMS			
Propranolol	Screening phase Through Day 28	Maximum of 40 mg/day				
Sleep Medication	Day 1 and Day 28	No restrictions ^a	Not within 8 hours prior to Cogstate test			
zolpidem, zaleplon, or eszopiclone for insomnia						

^a Allow nighttime use only (prn); exclude regular use; exclude daytime use; exclude use within 12 hours of a study visit Abbreviations: AIMS = Abnormal Involuntary Movement Scale; BARS = Barnes Akathisia Rating Scale; mg = milligram; PANSS = Positive and Negative Syndrome Scale; SAS = Simpson-Angus Scale

During the End of Stabilization period, the use of lorazepam, benztropine, and propranolol is not restricted.

Smoking is allowed, under supervision.

Confidential Page 50 of 102

Table 6.3 below provides a select list of CYP2D6 inhibitors and CYP3A4 inhibitors and inducers that are prohibited within 14 days of randomization and for the duration of the trial.

Table 6.3: Selected CYP2D6 Inhibitors and CYP3A4 Inhibitors and Inducers Prohibited During the Trial

Selected CYP2D6 Inhibitors	
Celecoxib	Methadone
Chloroquine	Moclobemide
Chlorpheniramine	Paroxetine
Clemastine	Pyrilamine
Clomipramine	Quinidine
Fluoxetine	Terbinafine
Halofantrine	Tripelennamine
Hydroxyzine	
Selected CYP3A4 Inhibitors	
Amiodarone	Fluvoxamine
Amprenavir	Indinavir
Aprepitant	Itraconazole
Chloramphenicol	Ketoconazole
Cimetidine	Nefazodone
Clarithromycin	Nelfinavir
Clotrimazole (if used orally)	Quinupristin/Dalfopristin
Delavirdine	Ritonavir
Diltiazem	Saquinavir
Erythromycin	Troleandomycin
Fluconazole	Verapamil
Selected CYP3A4 Inducers	
Carbamazepine	Phenytoin
Dexamethasone	Primidone
Efavirenz	Rifampin
Nevirapine	St. John's Wort
Oxcarbazepine	Troglitazone
Phenobarbital	

Abbreviations: CYP = cytochrome P450

Confidential Page 51 of 102

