Vital Signs ^t	X	X		X		X		X		X		
Adverse Events ^u	X	X	X	X	X	X	X	X	X	X	X	X
Other												
Study Drug Dosing		X	X	X	X	X	X	X	X	X		
PK Sample Collection ^v		X		X				X				
Restart Standard Antipsychotic ^w											X	

a. Screening begins when the ICF is signed and will take place between Day -7 and Day -1; up to a 7-day extension of the screening phase is allowed, if necessary with the approval of the Medical Monitor; screening procedures should be initiated with a sufficient amount of time allotted in order to obtain central laboratory results and ECG results from the central reader prior to randomization. Review of inclusion/exclusion criteria at Baseline will be based on assessments performed during Screening. Hospitalization will begin with the signing of the ICF for patients who are not already hospitalized at the initial Screening Visit.

Confidential Page 55 of 102

Each patient may receive the QD administration of study treatment. No other assessments are scheduled; however, AEs observed or reported, and concomitant medications may be recorded. In case of an AE, an unscheduled visit may be conducted at the discretion of the PI.

c. Stabilization Period is up to 5 days.

d. The Screening assessments to be audio recorded include the MINI 7.0.2, PCRS and SCI-PANSS and are submitted to an independent central reviewer for review and eligibility confirmation.

^{e.} Includes full psychiatric history, DSM-5 diagnosis of schizophrenia, and MINI 7.0.2.

Washout of prohibited medications begins after signing the ICF and after diagnosis of Schizophrenia is confirmed by MINI. Details of medications requiring washout and guidance for washout time required are provided in Appendix 14.4. Prohibited and restricted medications are listed in Table 6.3:

g. Urine drug screen (full panel including opioids) and a blood alcohol test are required at the designated times, but either or both can be conducted at any time during the trial at the discretion of the Investigator.

h. At Screening, Baseline, and final endpoint, SCI-PANSS and CGI-S will be evaluated by a local site rater with central supervision via independent, central review.

SCI-PANSS will be audio recorded at any visit where they are administered. SCI-PANSS assessment should be preceded by the PCRS. Patients with improvement of ≥20%

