Of the TEAEs definitely related to study drug, there were 11 cases of elevated prolactin (≥100 μg/L; 50 mg QD, N = 3; 10 mg QD, N = 1; 100 mg QD, N = 1; 150 mg QD, N = 1; 50 mg BID, N = 2; 100 mg BID, N = 1; 75 mg BID, N = 2), 4 cases of moderate dystonia (200 mg QD, N = 1; 100 mg BID, N = 2; 75 mg BID, N = 1), and 1 case of mild ECG QTcF prolongation (458 msec, 200 mg LB-102 QD) that were all resolved with either no course of action (prolactin increase and QTcF interval prolongation) or concomitant medications (dystonia). Due to 2 TEAEs in the same SOC (acute dystonic reaction), treatment was halted in all healthy volunteers taking 100 mg LB-102 BID (Cohort 7) and the 2 healthy volunteers in Cohort 7 taking placebo. As a result, the SRC decided to reduce the dose for Cohort 8 to 75 mg LB-102 BID. Additionally, because QTcF interval was fairly prolonged from pre-dose values (20-46 msec) in all healthy volunteers taking 200 mg LB-102 QD (Cohort 4), the dosage for Cohort 5 was reduced to 150 mg LB-102 QD. Of the TEAEs probably or possibly related to study drug, there were 4 cases of nausea (100 mg LB-102 QD, N = 1; 200 mg LB-102, N = 1; 100 mg

Confidential Page 93 of 102

LB-102 BID, N = 1; 75 mg LB-102 BID, N = 1) and 1 case of vomiting (100 mg LB-102 BID), urticaria (100 mg LB-102 QD), gastroesophageal disease (200 mg LB-102), insomnia (75 mg LB-102 BID), dizziness (75 mg LB-102 BID), and somnolence (75 mg LB-102 BID).

Vital signs and physical examination results were largely unchanged from Baseline. Other than increases in prolactin, chemistry laboratory results were also relatively unchanged throughout study treatment. C-SSRS did not change during study treatment.

Pharmacokinetics Results

In Part A (SAD), LB-102 was rapidly absorbed and LB-102 concentration generally declined from peak in an apparent biphasic manner. The estimates of mean t_½ of LB-102 generally ranged from 11.993 to 14.146 hours; exposure (as measured by C_{max}, AUC_{0-t}, and AUC_{0-inf}) increased in a slightly greater than dose-proportional manner. Mean C_{max} ranged from 24.1 ng/mL at the lowest dose of 10 mg LB-102 to 975.667 ng/mL at the highest dose of 200 mg LB-102. Mean AUC_{0-t} ranged from 221.911 h•ng/mL at the lowest dose to 6709.821 h•ng/mL at the highest dose. Mean AUC_{0-inf} ranged from 252.637 h•ng/mL at the lowest dose to 7002.109 h•ng/mL at the highest dose. Apparent clearance (CL/F) appeared to decrease as dose increased (42.44 L/h to 28.89 L/h).

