
 
• Taking a prohibited medication prior to Week 4
 
• Starting an emergency treatment prior to Week 4
 
 
All of these intercurrent events (ICEs) will be handled via a composite strategy, i.e. patients will be considered as non-responders
	
Missing data at Week 4 because of discontinuation due to ‘Lack of Efficacy’ or a drug-related AE will be imputed as non-responders. For all other missing data, the PANSS total score imputed for the primary analysis of the primary endpoint will be dichotomized as responders or not.
 
As a sensitivity analysis, all missing data will be imputed as non-responders.

Population-level summary measure	Analysis approach
Difference between patients treated with LB-102 (50 or 75 mg QD) and those treated with matching placebo in the PANSS response rate at Week 4 post-baseline.	
This endpoint will be analyzed using a logistic regression model including treatment and Baseline PANSS score as covariates to estimate the odds ratio (OR) of response of LB-102 (50 or 75 mg QD) vs placebo. The model will be fit separately to all imputed datasets and results pooled across imputations to obtain one single treatment effect estimate alongside 95% CI.
 
The same model will also be fit for the sensitivity analysis and a single OR (alongside its 95% CI).

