#### ***5.11.5.5 Response rate, defined as a reduction of $\geq 20\%$ from Baseline in PANSS total score at Week 4***

As described in Table 2, prior to analysis the PANSS score data imputed under a MAR mechanism will be dichotomized as being a responder or non-responder, and then missing data due to discontinuation because of lack of efficacy or drug-related AE as well as any data collected after any relevant ICE (start of emergency or prohibited treatment prior to Week 4) will be imputed as non-responders. The resulting dataset will be analyzed using a logistic regression using the response status at Week 4 as a response and baseline PANSS score, and treatment as covariates, using the below sample SAS code:

```
ods output Diffs = <output-dataset>;
proc logistic data =  descending;
  by _imputation_;
  class trt01p (ref = 'Placebo');
  model response = trt01p baseline / link = logit;
  lsmeans trt01p / diff ilink om oddsratio;
run;
```

From the above, the log odds ratio alongside its standard error will be estimated and then pooled across imputed datasets to return one single estimate, which will be exponentiated (alongside its 95% CI) to obtain an OR for each treatment arm. The proportion of responders at day 28 will also

be descriptively summarized (based purely on observed data), with an approximate 95% CI reported, derived using the following sample SAS code:

```
ods output RiskDiffCol2 = <output-dataset>;
proc freq data = ;
  table trt01p*response / riskdiff (column = 2);
run;
```

This endpoint will also be analyzed by imputing all missing data as non-responders and fitting the same logistic regression as above, from which the OR for each arm will be estimated.

Response status will be listed in the general PANSS listing.

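### The PANSS responder rule counts any prohibited or emergency medication before Week 4 as failure, whatever the drug or its indication, and the protocol can be read as defining the events differently

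*SAP*

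**What the plan says.** SAP Table 2 (section 2.3) defines the responder estimand with two intercurrent events. One is "Taking a prohibited medication prior to Week 4"; the other is the start of an emergency treatment in the same period. Both "will be handled via a composite strategy, i.e. patients will be considered as non-responders". SAP 5.11.5.5 puts this into practice: "any data collected after any relevant ICE (start of emergency or prohibited treatment prior to Week 4) will be imputed as non-responders". Discontinuations for lack of efficacy or a drug-related adverse event also become non-responses, but as a rule for missing data.

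The protocol describes prohibited drugs in two places:

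- Protocol 6.7 bars psychotropic medication apart from a short list of named exceptions.
- The same section contains Table 6.3, titled "Selected CYP2D6 Inhibitors and CYP3A4 Inhibitors and Inducers Prohibited During the Trial". The washout footnote to the schedule in Protocol 7.1 points there: "Prohibited and restricted medications are listed in Table 6.3".

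Emergency treatment appears in Protocol 6.7 only as an approval rule: "Any patient requiring emergency treatment with prescription or nonprescription medication during the screening phase through the EoS Visit will be approved by the Investigator".

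Protocol 10.4.4.3 first makes a patient a responder only if the 20% criterion is met and none of the previously listed events has happened. Its next sentence says that, for this endpoint, the relevant events are study discontinuations related to treatment.

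**The concern.** A composite strategy is useful when the event is itself evidence on the outcome, as when another antipsychotic is added because the patient is not improving. The SAP wording goes further. Someone whose PANSS total falls from 100 to 60 (a 40% reduction) and who took erythromycin for an infection in Week 2 is a non-responder by rule. The endpoint then partly records intercurrent illness.

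The two documents may also not define the same endpoint. If the second sentence in Protocol 10.4.4.3 governs, that patient is a responder under the protocol and a failure under the SAP. An undefined emergency-treatment event adds a judgement that would have to be made patient by patient, with no written rule.

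**Working it through.** **1. Which events the rule catches.** Setting the texts side by side:

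| Event before Week 4 | Source | Evidence of antipsychotic failure? | SAP response status |
|---|---|---|---|
| Non-permitted psychotropic | Protocol 6.7 | Often yes | Non-responder |
| Psychiatric drug in Table 6.3 (e.g. fluoxetine, paroxetine, carbamazepine; also in Appendix 14.4) | Protocol 6.7 | Possibly | Non-responder |
| Non-psychiatric drug in Table 6.3 (e.g. erythromycin, fluconazole, cimetidine) | Protocol 6.7 | No | Non-responder |
| Emergency treatment, any reason | Not defined | Depends on indication | Non-responder |

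No text requires withdrawal because such a drug was taken. Protocol 10.4.1 lists receipt of a prohibited concomitant treatment as a protocol deviation, and the SAP rule itself refers to data collected after the event. A patient can therefore have a valid Week 4 PANSS that is overridden.

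**2. Whether another planned analysis removes the problem.** The sensitivity analysis in SAP Table 2 and 5.11.5.5 changes only how missing values are scored. The descriptive proportions in 5.11.5.5 use observed data, but the text does not say whether the override applies to them, and they are not the modelled odds ratio.

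**3. Protocol against SAP.** Protocol 10.4.4.1 lists two medication events and no discontinuation event. The second sentence in 10.4.4.3 can replace those events with treatment-related discontinuations, or it can only say which discontinuations count in addition. The SAP agrees with the second reading and departs from the first. SAP section 8 says that treatment discontinuation was removed as an event from Tables 1 and 2; it declares no difference over medication events for response.

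**4. Size.** The plan gives no response rate, no rate of such medication use and no power for this endpoint, so there is no planned figure to reproduce. All inputs below are assumptions.

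- Response if only events informative about psychosis count: pA = 50% on LB-102, pP = 35% on placebo.
- Share with a non-psychiatric event: qA and qP, independent of response.
- Observed response = p(1 − q); crude odds ratio = [a/(1 − a)] / [b/(1 − b)], where a and b are the observed active and placebo proportions.

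| qA / qP | LB-102 | Placebo | Difference (points) | Odds ratio |
|---|---|---|---|---|
| 0 / 0 | 50.0% | 35.0% | 15.0 | 1.86 |
| 2% / 2% | 49.0% | 34.3% | 14.7 | 1.84 |
| 5% / 5% | 47.5% | 33.25% | 14.25 | 1.82 |
| 10% / 10% | 45.0% | 31.5% | 13.5 | 1.78 |
| 8% / 3% | 46.0% | 33.95% | 12.05 | 1.66 |
| 3% / 8% | 48.5% | 32.2% | 16.3 | 1.98 |

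For example, at 5% in both arms: 0.50 × 0.95 − 0.35 × 0.95 = 0.1425, and (0.475/0.525) / (0.3325/0.6675) = 1.82.

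With 50% v 30% instead, the odds ratio is 2.33 with no such events, 2.05 with 10% active and 5% placebo, and 2.45 with those rates reversed.

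**The case against.** The best defence is that the SAP states its estimand openly: these events classify as non-response, and nothing in the documents says the composite is meant only for psychosis rescue. Use may be rare, since patients are inpatients, take nothing without the Investigator's approval, and the Medical Monitor is contacted within 24 hours. The endpoint has no multiplicity control, Protocol 10.4.4.3 calls it exploratory, and the primary endpoint handles the same events by treatment policy. All of this stands and limits the consequence. It does not explain why an antifungal should count as antipsychotic failure, and it does not settle the protocol conflict.

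A reader might infer four stronger claims that the documents do not support:

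- **That the prohibited list consists only of enzyme inhibitors and inducers.** Protocol 6.7 also bars most psychotropics, and Table 6.3 itself contains psychiatric drugs. The schedule footnote is a loose cross-reference: it places restricted drugs in Table 6.3 too, although the dose limits are in Table 6.2.
- **That recovered patients are scored as failures.** The criterion is a reduction of at least 20%, which is response and not recovery.
- **That emergency treatment means non-psychiatric treatment.** It is simply undefined.
- **That LB-102 responders would be lost preferentially.** The Phase 1 support is one case of urticaria at 100 mg QD and one of gastroesophageal disease at 200 mg, in healthy volunteers. Table 2 compares 50 and 75 mg with placebo, and nothing shows that either volunteer took a Table 6.3 drug. The 8% v 3% split that costs about a fifth of the difference (15.0 to 12.05 points) is invented; reversing it raises the difference to 16.3.

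**Conclusion.** The point holds as a defect in the definition of a secondary endpoint. Followed literally, the SAP misclassifies patients who meet the 20% criterion and took a non-psychiatric prohibited drug, or emergency treatment for a reason unrelated to psychosis. The protocol can be read as not counting medication events for this endpoint at all, and that possible difference is undeclared.

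The numerical effect is probably modest if use is low and similar across arms: at assumed equal rates of 2% to 10%, the 15-point difference loses 0.3 to 1.5 points. With unequal rates the direction is unknown. These figures rest on assumed response rates and on independence between the event and response; only events among patients who would otherwise be responders change anything. The primary analysis is not touched.

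**What to change.** Before unblinding:

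1. Reconcile Protocol 10.4.4.3 with SAP Table 2 and 5.11.5.5, and record the outcome in SAP section 8.
2. For the responder endpoint, restrict the composite medication events to prohibited psychotropics and to emergency treatment given for psychotic symptoms or agitation. Define emergency treatment in the SAP.
3. Assign the flags by blinded review of coded concomitant medications and the reason for use, which Protocol 6.7 already requires to be recorded.
4. Handle other prohibited or emergency medication by treatment policy, as for the primary endpoint.
5. Keep the present all-medication rule as a sensitivity analysis, and state whether the observed-data proportions apply the override.

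The cost is SAP wording, one blinded review and one extra run of the logistic model. The small downside is that a few dual-use drugs need a classification decision. This changes the analysis definition only, not which medications are allowed in the trial.

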## 5.11.6 Exploratory Endpoints

All exploratory endpoints will be analyzed on the ITT analysis set. As described in Section 5.11.2, should the ITT and mITT analysis sets overlap substantially, secondary endpoints will only be analyzed on the mITT analysis set.

### 5.11.6.1 Effect of LB-102 on Cogstate test scores

Summaries for the actual and change from Baseline values for each of the Cogstate test scores (International Shopping List Test, Detection Test, Identification Test, One Back Test and Modified Groton Maze Learning Test) will be provided by treatment group. In addition, an analysis of covariance (ANCOVA) model will also be fit including pooled study site and treatment as categorical covariates and baseline Cogstate test score as continuous covariate and change from baseline to day 28 in the Cogstate test score as the response. LS means and their differences alongside 95% CIs and p-values for the comparison of active arms vs placebo will be reported. The following sample SAS code will be used:

```
ods output estimates = est LSMeans = lsm diffs = diff;
proc mixed data =  plots (only) = studentpanel(marginal);
  by test;
  class trt01pn siteid;
  model chg = trt01pn siteid base / ddfm = kr;
  lsmeans trt01pn / diff cl;
run;
```

All Cogstate test score results will also be listed.

## 5.11.7 Multiplicity

Results from the analysis of the primary endpoint across the 50 and 75 mg doses will be adjusted for multiplicity using a standard Hochberg procedure. This approach involves ranking the P values from the smallest ( $P_{(1)}$ ) to the largest ( $P_{(2)}$ ) and then comparing  $P_{(2)}$  against 0.05 and if this hypothesis is rejected then reject also the one associated with  $P_{(1)}$ , otherwise  $P_{(1)}$  is further tested

at a local 0.025 two-sided level, and if the test is significant at this level than the null hypothesis associated with it is rejected, whereas the one associated with  $P_{(2)}$  is retained.

## 5.12 Pharmacokinetic Analyses

Blood samples for determination of plasma concentrations of drug will be collected on Day 1, 8 and 21 at the following time-points: pre-dose (only at Day 1), 15 minutes, 30 minutes, 1, 2, 3, 4, 8, and 24 hours post dose. Concentration-time data will be tabulated by nominal (planned) time, analyte, and treatment using descriptive statistics. For presentation of the individual data and summary statistics, concentrations below the limit of quantitation (BLQ) will be set to half the lower limit of quantitation (LLOQ).

Individual patient and mean plasma concentration-time data will be presented graphically on linear and semi-logarithmic scales. Mean data will be plotted using nominal sample times, and individual data will be plotted using actual times.

The following PK parameters will also be summarized by analyte and treatment using descriptive statistics: area under the concentration-time curve from time zero to time (AUC0-t), area under the concentration-time curve from time of dosing up to 24 hours (AUC0-24), area under the concentration-time curve from time zero to infinity (AUC0-inf), area under the concentration-time curve from time 0 to the last available sampling time (AUClast), area under the concentration-time curve extrapolated from time t to infinity as a percentage of the total AUC (AUC%extrap), oral clearance (CL/F), maximum concentration (Cmax), time to reach Cmax (Tmax), terminal elimination rate constant ( $\lambda_z$ ), and apparent terminal half-life (t1/2).

Dose proportionality will be assessed by using a power model separately for the Cmax and AUClast separately for each applicable visit. In this model the log-transformed PK parameter of interest will be considered as the response variable and the log-transformed dose (i.e. 50, 75 and 100 mg) will be the only model covariate. The model will be fit using the following sample SAS code:

```
ods output parameterestimates = parms;
proc mixed data =  plots = none;
  by visit;
  model logaval = logdose / ddfm = kr;
run;
```

From the above model the slope estimate  $\beta$  will be derived alongside its 90% confidence interval, and dose proportionality will be met if the confidence intervals lie entirely within this range:

$$1 + \frac{\ln(\Theta_L)}{\ln(r)} \text{ to } 1 + \frac{\ln(\Theta_H)}{\ln(r)}$$

Where r is the ratio between the largest and the smallest dose ( $= 100/50 = 2$ ) and  $\Theta_L$  and  $\Theta_H$  are defined as 0.8 and 1.25 (similar to standard bioequivalence margins). As such the dose-proportionality range for the slope parameter is 0.678 to 1.322.

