10.4.6 Pharmacokinetics

Data from patients who participated in the study will be included in the PK analysis. Patients with missing sample concentrations will be included in the PK analyses, provided their PK parameters can be adequately characterized based upon the remaining data.

Deviation from procedures described in this protocol that impact the quality of data required to meet the objectives of the study will be documented and may result in the exclusion of PK data from the analyses for a particular patient. This includes any deviations or events that would invalidate the evaluation of the PK. Examples of deviations and events that could result in the exclusion of PK data from the analyses include emesis after dosing (within the predetermined time), sample processing, or assay errors that lead to inaccurate bioanalytical results. Other deviations or events that do not disqualify data from analyses may require minor adjustments to calculations. If these occur, data analyses will be adjusted and documented accordingly such that conclusions are not biased. An example of such an event includes, but is not limited to, minor deviations between the actual and scheduled time of sample collection.

Other PK analyses may be performed as appropriate.

Plasma concentrations of LB-102 will be measured during the study and PK parameters derived using noncompartmental or compartmental methods as appropriate. The following PK parameters (as appropriate) will be calculated: AUC_{0-t} , AUC_{0-24} , AUC_{0-inf}

No value for λ_z , AUC_{0-inf}, CL/F, or $t_{1/2}$ will be reported for cases that do not exhibit a terminal log-linear phase in the concentration versus time profile.

No PK parameters will be calculated for patients with no detectable concentrations for 2 or fewer time points.

Individual and mean plasma concentration-time curves (both linear and log-linear) will be included in the final report.

PK parameters of LB-102 and metabolites will be summarized by cohort using descriptive statistics

Figures will be created to display mean and individual patient LB-102 and concentration-time curves in plasma on both a linear and logarithmic scale. Dose proportionality will be assessed using linear regression, or another acceptable approach.

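### The dose-proportionality model uses AUClast, so a profile missing its 24-hour sample enters roughly 30% low; AUC0-24 with a stated completeness rule avoids this cheaply

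*SAP*

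**What the plan says.** SAP 5.12 states: "Dose proportionality will be assessed by using a power model separately for the C max and AUC last separately for each applicable visit". AUClast is the "area under the concentration-time curve from time 0 to the last available sampling time", so its upper limit belongs to the patient, not to the design. Post-dose samples are planned at "15 minutes, 30 minutes, 1, 2, 3, 4, 8, and 24 hours post dose". The parameter list in the same section also contains the "area under the concentration-time curve from time of dosing up to 24 hours (AUC 0-24"), but that parameter is only summarized. The log-log slope is estimated "alongside its 90% confidence interval", and proportionality is concluded when the whole interval lies inside a range built from limits that "are defined as 0.8 and 1.25" and from r, the "ratio between the largest and the smallest dose".

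SAP 5.1.5 admits to the PK Analysis Set anyone who provides concentration samples and sets no completeness requirement. Protocol 10.4.6 says: "Patients with missing sample concentrations will be included in the PK analyses, provided their PK parameters can be adequately characterized" from what remains. It also allows PK data to be excluded when a deviation affects their quality, and calculations to be adjusted so that conclusions are not biased. It asks for dose proportionality by linear regression or another acceptable approach and names no exposure metric.

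**The concern.** The power model regresses log exposure on log dose, so every response should cover the same interval. With the last two planned samples at 8 and 24 hours, losing the final one shortens the AUC to 8 hours. On Days 8 and 21, under once-daily dosing, the natural comparison is exposure over the 24-hour dosing interval.

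No rule clearly removes such a profile. The protocol's condition concerns whether parameters can be characterized, and an AUC to the last sample can still be computed from a profile that ends at 8 hours. The slope would then carry sampling completeness as well as exposure. The 100 mg arm is the sensitive place, because few PK patients are expected there and each has high leverage.

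**Working it through.** **The plan's own range.** 1 + ln(0.8)/ln(2) = 0.678 and 1 + ln(1.25)/ln(2) = 1.322. The SAP's figures reproduce; the allowed deviation from a slope of 1 is 0.322.

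**Inputs.** Protocol Table 14.1 (single dose, six healthy volunteers per dose), arithmetic means:

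| | 50 mg | 100 mg |
|---|---|---|
| AUC0-24 (ng·h/mL) | 1336.105 | 2303.664 |
| AUC0-inf (ng·h/mL) | 1595.938 | 2809.785 |
| λz (1/h) | 0.0592 | 0.0521 |

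**Share of AUC0-24 lost without the 24-hour sample.** Assume the terminal phase has begun by 8 hours.

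- C24 = (AUC0-inf − AUC0-24) × λz. At 50 mg: 259.8 × 0.0592 = 15.4. At 100 mg: 506.1 × 0.0521 = 26.4.
- C8 = C24 × exp(16λz) = 39.7 and 60.7.
- AUC8-24 = (C8 − C24)/λz = 410 and 659.
- Single-dose loss: 410/1336.1 = 30.7% and 659/2303.7 = 28.6%.
- Steady-state loss by superposition: [AUC8-24/(1 − exp(−24λz))]/AUC0-inf. At 50 mg: (410/0.758)/1595.9 = 33.9%. At 100 mg: (659/0.714)/2809.8 = 32.9%.

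AUC0-8 is therefore about 66–71% of AUC0-24. Protocol 14.2.1 describes the decline as biphasic. An illustrative biexponential profile gave losses of 23–39%, depending on dose and trapezoid rule.

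**Effect of one truncated profile on the slope.** The Protocol Table 7.1 footnotes take PK from the first 60 randomized patients. At 3:3:3:1 this implies about 18 on placebo and 18/18/6 on 50/75/100 mg. With x = ln(dose), the mean is 4.185 and Sxx = 2.717. Shift = (x − 4.185) × ln(1 − loss)/2.717.

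| Arm losing the sample | Loss 28.6% | Loss 33.9% |
|---|---|---|
| 50 mg | +0.034 | +0.042 |
| 75 mg | -0.017 | -0.020 |
| 100 mg | -0.052 | -0.064 |

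At 100 mg the shift is 16–20% of 0.322 (0.052/0.322 and 0.064/0.322).

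**Room left after sampling error.** The whole 90% interval must fit. At an assumed between-patient CV of 20%, the log-scale SD is √ln(1.04) = 0.198 and the half-width is 1.684 × 0.198/√2.717 = 0.202. That leaves 0.322 − 0.202 = 0.120. At a 33% loss, one truncated 100 mg profile shifts the slope by -0.062, about half of that room; two use all of it. The Phase 1 geometric CVs of AUC0-24 were 12.9% at 50 mg and 26.5% at 100 mg.

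**Chance of concluding proportionality when the true slope is 1.** Simulation, 20,000 runs per scenario, 33% loss per truncated profile:

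| Scenario | Truncated AUClast kept | Profile left out |
|---|---|---|
| CV 20%, complete data | 68% | – |
| CV 20%, 10% missing at random in every arm | 46% (mean slope 1.00) | 60% |
| CV 20%, two of six at 100 mg | about 40% | about 58% |
| CV 13%, two of six at 100 mg (98% if complete) | about 70% | about 97% |
| CV 26.5%, two of six at 100 mg | 16.8% | 17.5% |

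**The case against.** A reader might infer that AUClast biases the slope systematically, most likely downwards. The documents do not support that. The sign depends on the arm that loses the sample, and equal missingness leaves the mean slope at 1.00. There may also be little missingness: patients are inpatients throughout treatment (Protocol 7.1), dosing is supervised (6.6), and the 24-hour draw has a 15-minute window either side and must precede the next dose (8.3). For complete profiles AUClast and AUC0-24 cover the same nominal interval and the point disappears.

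A reader might also infer that the protocol keeps every patient with missing samples. It does not: inclusion is conditional, and section 10.4.6 offers routes to exclude or adjust. Those routes are general, however, and none names a profile that ends at 8 hours.

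Nor is swapping the parameter name enough by itself. The completeness restriction does the work; AUClast under the same restriction would be essentially the same analysis. AUC0-24 extrapolated from a λz fitted at 3, 4 and 8 hours still fell about 8–9% short in the illustrative profile.

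Finally, PK appears in none of the listed objectives or endpoints, and AUC to the last sample is consistent with how Phase 1 single-dose exposure was described. These points set the importance low. They do not remove the gap: the plan does not say what happens when the 24-hour sample is missing, and the stated metric handles that case poorly.

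**Conclusion.** The point holds as a conditional weakness of a low-stakes analysis. If a 24-hour sample is missing and the profile stays in, it enters roughly 30% low. One such profile shifts the slope by about -0.05 to -0.06 at 100 mg, -0.02 at 75 mg, or +0.03 to +0.04 at 50 mg. Missingness spread evenly across arms costs precision rather than causing a tilt. At a CV of 20% and 10% missing, the chance of meeting the range drops from 68% to 46%, of which leaving those profiles out recovers to 60%.

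These sizes rest on an assumed 18/18/6 split, an assumed CV, single-dose Phase 1 means, and a terminal phase that has begun by 8 hours. The 10% rate is an illustration, since the documents give none. At a CV of 26.5% the gain from leaving profiles out is small.

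**What to change.** In SAP 5.12, use AUC0-24 instead of AUClast in the power model for Days 1, 8 and 21. Add one clause: a profile without a 24-hour sample is left out of the AUC model for that visit and is not extrapolated from the samples up to 8 hours. Leave the Cmax model, the 90% interval and the range 0.678–1.322 unchanged.

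The cost is one substituted parameter, already derived, and one sentence. The downside is that incomplete profiles leave the AUC model, which at 100 mg could mean losing one or two of about six. In the scenarios simulated, leaving them out gave a pass rate at least as high as keeping them truncated.
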